I have read and agreed to the protocol proposed in this document, and acknowledge the relevant content thereof. During the trial, I will strictly comply with the laws, regulations, and relevant rules of the People's Republic of China, fulfill my duties as a research participant, and adhere to confidentiality requirements.

Research institution: The First Affiliated Hospital of
Zhejiang University School of Medicine

Name of investigator: [name]

Researcher Position: Associate Chief Physician

Researcher's signature:

Date of signature:

scenario summary

Study name	Prospective clinical study of 18F-FAPI PET imaging in the diagnosis of lung cancer
Study protocol	This study adopted a prospective, multicenter research design. It aimed to evaluate the diagnostic research and exploration of 18F-FAPI PET/CT in lung cancer patients. A total of 120 subjects were planned to be enrolled from three centers nationwide (The First Affiliated Hospital of Zhejiang University School of Medicine, Zhejiang Provincial People's Hospital, and Shulan Hangzhou Hospital).
research design	perspective study
Number of research centers	3
sample capacity	120
indication	patients with suspected or confirmed lung cancer who have undergone 18F-FAPI PET/CT
purpose of research	The purpose of this study was to evaluate the diagnostic efficacy and prognostic value of 18F-FAPI PET/CT in lung cancer.
primary end point	Diagnostic efficacy of 18F-FAPI PET/CT in lung cancer (sensitivity, specificity, accuracy)
Selection criteria	(1) Patients suspected or diagnosed with lung cancer (2) 18F-FAPI PET/CT has been performed.
exclusion criteria	(1) Concurrent presence of other active malignant tumors or a history of other malignant tumors within the past 5 years; (2) Severe uncontrollable diseases or active infections; (3) Ineligible participants who cannot provide informed consent for the study; (4) Pregnant and lactating women.
study termination criteria	1. Achieve the research objectives; 2. Occurrence of severe adverse events
18F-FAPI Instructions	The Nuclear Medicine PET Center holds a Class IV Certificate for Radioactive Drugs, enabling independent production and development of radiopharmaceuticals for scientific research. 18F-FAPI is a routinely performed tracer in our hospital, with over 1,800 cases of 18F-FAPI PET/CT scans completed to date, primarily including pancreatic cancer, gastric cancer, colorectal cancer, and head and neck tumors.
Visit Plan	For patients under treatment and follow-up at this hospital, no in-person visits are required; relevant data can be obtained from the electronic medical record (EMR) system and imaging system of this hospital. For patients not receiving treatment at this hospital, a telephone follow-up protocol is implemented to obtain relevant pathological results.

research report	The study plans to enroll 120 eligible patients within 3 years, followed up their pathological results, and conduct statistical analysis.
statistical analysis	Statistical analysis was performed using SPSS 17.0. The diagnostic sensitivity, specificity, and negative/positive predictive values were calculated using a four-cell table. The area under the ROC curve and the optimal cutoff value (SUV optimal cutoff) were evaluated by ROC curve analysis. The consistency between 18F-FAPI PET diagnosis and pathological diagnosis was assessed using the kappa test. A p-value <0.05 was defined as statistically significant.

English abbreviation reference

PET	Positron emission tomography
CT	Computed tomography
ROC	Receiver operating characteristic curve
FAPI	Fibroblast activation protein inhibitor

1 Research Background

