2.1.4 Evaluation of 18F-FAPI PET/CT in Predicting Lung Cancer Prognosis

Based on TNM staging and PERCIST criteria, this study evaluates the post-treatment reassessment, efficacy prediction, and prognostic assessment (AUC comparison of PFS/OS) of 18F-FAPI PET/CT in lung cancer. The research will analyze the monitoring capability of 18F-FAPI PET/CT in assessing tumor response post-treatment

and its value in prognostic evaluation, aiming to provide clinicians with a more precise tool for assessing treatment efficacy. It tracks the time from diagnosis to specific events (e.g., CR, PR, SD, PD, recurrence, death) in lung cancer patients to identify influencing factors. Survival rates over time are plotted using Kaplan-Meier curves to visually compare survival differences across groups. Additionally, Cox proportional hazards model multivariate regression quantifies the contribution of factors such as age and pathological stage to survival risk, aiding clinical decision-making.

3 Mechanism of Action and Research Scope of 18F-FAPI PET/CT

18F (97% β^+ , $T_{1/2}=109.7$ minutes) is currently the most widely used radionuclide in PET/CT due to its chemical, physical, and nuclear properties, making it an ideal choice for peptide-based imaging. 18F-FDG is the most commonly used PET tracer in oncology, serving as the preferred modality for tumor diagnosis and therapeutic efficacy evaluation. However, 18F-FDG PET/CT exhibits relatively low sensitivity and specificity for tumors with low invasiveness, high differentiation, or mucinous tissue, while physiological uptake in organs such as the oropharynx and digestive tract often obscures tumor metabolism and uptake. Additionally, mediastinal and hilar lymph nodes still show a high rate of false positives on 18F-FDG PET, whereas 18F-FAPI PET/CT improves the specificity of lymph node diagnosis. Furthermore, compared to 68Ga-labeled tracers, 18F-labeled FAPI has better resolution potential due to its lower positron energy. Therefore, 18F-labeled FAPI holds significant clinical value and promising prospects.

4 Indications, Contraindications, and Precautions

4.1 Eligibility Criteria: Patients with suspected or confirmed lung cancer who have undergone 18F-FAPI PET/CT

4.2 Exclusion Criteria:

- (1) Concurrent presence of other active malignant tumors or a history of other malignant tumors within the past 5 years;
- (2) Severe uncontrollable diseases or active infections;
- (3) Ineligible participants for informed consent.

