5.3.3 Subject Loss to Follow-up

Lost to follow-up: Participants did not complete the specified follow-up period but did not 'formally' withdraw from the clinical trial.

If a participant fails to respond to three telephone follow-ups, a registered mail letter must subsequently be sent to the participant. If the participant does not respond to the letter, the participant will be considered as having "lost to follow-up" for current study visits or telephone contacts. The investigator must record this information on the original data sheet. The investigator must report this information to the relevant ethics committee in accordance with the procedures of their institution.

For cases with lost-to-follow-up, the reasons should be explained, and their e-CRF forms should be retained for review. No diagnostic efficacy statistical analysis will be performed, but the patients who undergo examinations may participate in safety analysis as appropriate.

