5.4 Study Endpoints

Primary endpoint: Diagnostic efficacy of 18F-FAPI PET/CT in lung cancer patients (sensitivity, specificity, accuracy)

secondary end points:

- ① Compare the diagnostic performance differences of 18F-FAPI PET/CT with CT, MR, and 18F-FDG PET imaging in clinical applications for lung cancer;
- ② Analysis of diagnostic differences in the subgroup of patients (pathological, genetic, etc.) using 18F-FAPI PET/CT;
- ③ Evaluation of 18F-FAPI PET/CT in predicting lung cancer prognosis.

6 Research Procedures and Operational Standards

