7.3 Statistical Methods

Statistical analysis was performed using SPSS 17.0. The diagnostic sensitivity, specificity, and negative/positive predictive values were calculated using a four-cell table. The area under the ROC curve and the optimal cutoff value (SUV optimal cutoff) were evaluated by ROC curve analysis. The consistency between 18F-FAPI PET/CT diagnosis and pathological diagnosis was assessed using the kappa test. A p-value <0.05 was defined as statistically significant.

Statistical analysis was performed using SPSS 17.0.

① Diagnostic performance evaluation, four-grid table index calculation:

Sensitivity = True positives / (True positives + False negatives) × 100%

Specificity = True Negative / (True Negative + False Positive) × 100%

Positive predictive value = true positive / (true positive + false positive)

Negative predictive value = true negative / (true negative + false negative)

② ROC curve analysis:

Calculate the area under the curve (AUC) and evaluate diagnostic performance (AUC>0.9 indicates excellent, 0.8-0.9 indicates good, 0.7-0.8 indicates moderate).

Determine the optimal cutoff for SUV using the maximum Youden index.

③ consistency check

The consistency between 18F-FAPI PET/CT and pathological diagnosis was evaluated using the Kappa coefficient.

Kappa>0.8: Excellent consistency;

0.6-0.8: High consistency;

<0.6: Consistency should be interpreted with caution.

Bilateral test, $p<0.05$ defined as significant difference.

④ survival analysis

Kaplan-Meier method:

Collect baseline PET parameters (lesion SUVmax, lesion SUVmean, MTV, LTV, bone marrow SUVmax, etc.), and plot PFS/OS curves according to treatment response (CR/PR vs. SD/PD), pathological response (e.g., MPR status), or PET parameter grouping (e.g., high/low SUVmax). Compare the significance of survival differences between groups using the Log-rank test ($p<0.05$).

Cox proportional hazards model:

Univariate analysis: Screening of clinical variables associated with PFS/OS (age, stage, SUVmax, MTV, etc.).

Multivariate analysis: Significant univariate variables ($p<0.1$) were included, with quantified hazard ratios (HR) and 95% confidence intervals.

Verify the proportional hazards assumption (Schoenfeld residual test).

8 Data Recording and Management

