8.1 Investigator Data Records

- 1) For all eligible participants who have signed the informed consent form, their relevant data and laboratory test results must be meticulously and thoroughly documented.
- 2) All imaging data were interpreted by two attending physicians with over 5 years of experience in nuclear medicine, and the chief physician provided the final consensus interpretation for any questionable cases.
- 3) Original data records, signed by the investigator and dated.

4) Confirm that all adverse events have been documented, and that serious adverse events have been reported and recorded in accordance with relevant procedures in a timely manner.

9 Expected Research Progress

Study recruitment period: 36 months

Observational study duration: This study was an observational study, with patient mortality serving as the endpoint of follow-up.

10 Adverse Event Assessment and Reporting

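### PFS and OS are to be analysed, but the Visit Plan gives no procedure for learning of deaths or progressions outside the hospital

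*Protocol*

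**What the plan says.** The Visit Plan (Protocol synopsis) sets two routes.

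- Patients under treatment and follow-up at the hospital need no in-person visits, because "relevant data can be obtained from the electronic medical record (EMR) system and imaging system of this hospital".
- For patients not treated there, "a telephone follow-up protocol is implemented to obtain relevant pathological results".

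The synopsis row on the research report describes the same scope: the study enrols 120 patients, "followed up their pathological results, and conduct statistical analysis".

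Other sections ask for more. Secondary endpoint 3 (sections 2.1 and 5.4) is "Evaluation of 18F-FAPI PET/CT in predicting lung cancer prognosis". Section 2.1.4 says of the study: "It tracks the time from diagnosis to specific events (e.g., CR, PR, SD, PD, recurrence, death) in lung cancer patients". Section 7.3 plans Kaplan-Meier curves, log-rank tests and Cox models for PFS and OS. Section 9 describes an observational study "with patient mortality serving as the endpoint of follow-up".

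Section 5.3.3 (Subject Loss to Follow-up) adds: "If a participant fails to respond to three telephone follow-ups, a registered mail letter must subsequently be sent to the participant". It does not say what those calls ask or when they are made.

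**The concern.** PFS and OS need, for each analysed patient, a dated vital status, a dated progression status and a last date on which both were known. The only described data sources do not reach that far. A patient treated elsewhere is called for pathology. A patient treated in-house is followed through one hospital's records, which need not show a death at home or a progression found at another institution.

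If the plan is followed as written, whether an event is seen depends on where the patient is treated. Patients treated elsewhere would either have their events missed or be censored at about the time of the pathology call. That loses events. It also makes censoring informative if place of treatment is related to prognosis. The log-rank comparisons and the hazard ratios for SUVmax, MTV and the other PET parameters would carry the problem. A statistical analysis plan can set censoring rules, but it cannot recover events that nobody asked about.

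**Working it through.** The protocol states no figure on this point, so the check is a comparison of its sections, followed by an illustration.

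**What the analysis needs against what is collected**

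| Item needed | Patients treated at the hospital | Patients treated elsewhere |
|---|---|---|
| Pathology | Hospital records | Telephone call |
| Progression or recurrence, with date | Hospital records, if it is seen there | No source named |
| Death, with date | Hospital records, if it is recorded there | No source named |
| Interval between checks | Not stated | Not stated |
| Common data cut-off | Not stated | Not stated |

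**Whether another section fills the gap**

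- Sections 2.1.4 and 9 state an intention to track events and to follow to death. They name no source, interval or contact.
- Section 5.3.3 (Subject Loss to Follow-up) uses calls and a letter to define loss to follow-up. It refers to a specified follow-up period, but none is specified.
- Section 6.2 lists follow-up medical records under history-taking at screening, which is not a scheduled outcome check.
- Section 10.4 sets documentation duties for deaths that are already known.

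None of these gives a way to find an outside event. The Visit Plan therefore conflicts with sections 2.1.4, 7.3 and 9.

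**Illustration of lost events**

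Inputs from the protocol: 120 patients; 36 months of recruitment (section 9); five-year survival of 19.7% for lung cancer in general (section 1.1); 80, 20 and 20 patients by centre (section 7.1).

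Assumptions of this review: constant hazard; survival time counted from enrolment; uniform accrual; every patient has the general lung-cancer hazard; analysis at calendar month 36; a share f of the deaths is missed, whatever the prognosis of those patients.

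1. Hazard: −ln(0.197)/5 = 0.325 per year. Over 3 years this is 0.975, and exp(−0.975) = 0.377.
2. Expected share dead at month 36 under uniform accrual: 1 − (1 − 0.377)/0.975 = 0.361.
3. Expected deaths: 120 × 0.361 = 43.
4. Recorded deaths: 43.3 × (1 − f). Power for an assumed hazard ratio of 2 with a 50:50 split and two-sided 0.05 (Schoenfeld): Φ(√(D/4) × ln 2 − 1.96), where D is the number of deaths.

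| Share missed, f | Recorded deaths | Power |
|---|---|---|
| 0 | 43 | 63% |
| 10% | 39 | 58% |
| 20% | 35 | 53% |
| 33% | 29 | 46% |

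The 33% is 40/120, the patients from the two smaller centres. It applies only if 'this hospital' means the lead centre alone. The 10% and 20% are arbitrary points of the range.

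**The case against.** The strongest reply is that the protocol plainly means to follow these patients. Section 2.1.4 says events are tracked, section 9 runs follow-up to death, and section 5.3.3 has a general telephone and letter procedure that is not limited to pathology. Patients followed in-house would normally have progression noted in their records, and the words used for that route are open-ended. This shows intent and stands to that extent. It does not supply a procedure, and where the Visit Plan does fix the content of the calls, it names pathology alone.

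A reader might also infer more than the text supports:

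- *That in-house patients have no contact.* The Visit Plan rules out only a requirement for in-person visits.
- *That outside deaths and progressions will certainly go unrecorded.* The stated intent to track them speaks against this. What can be said is that no means of doing so is given.
- *That all 120 patients enter the survival analysis.* Section 7.3 does not say so, and section 5.3.1 admits suspected cases, some of whom may prove benign.
- *That one third of patients are affected.* The Visit Plan divides patients by place of treatment, not by recruiting centre, and does not define 'this hospital'. If it means each site, the 40 patients at the other centres are covered by their own records when treated there.
- *That OS will be overstated by a known amount.* With f = 20%, 33% or 50% carried as alive, three-year OS of 0.38 would be recorded as f + (1 − f) × 0.377 = 0.50, 0.58 or 0.69. No section says that such patients are carried as alive. Under ordinary censoring at last contact, the first loss is of events.
- *That place of treatment is tied to stage or prognosis.* This is plausible, but the protocol gives no data on it.

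**Conclusion.** The point holds as an internal inconsistency with practical consequences. The stated data routes do not provide for what the PFS and OS analyses require, and the term that separates the two routes is undefined in a three-centre study. Left as it is, ascertainment for secondary endpoint 3 varies with place of treatment, events are lost, and censoring could be informative.

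It should be corrected, but it does not threaten the main result: the primary diagnostic endpoint needs pathology, which both routes can supply.

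No size can be given from the protocol. The fall from 43 to 29 deaths is illustrative only. It rests on a general lung-cancer hazard applied to a group that includes suspected cases, an analysis date that the protocol does not set, equal risk inside and outside the hospital, and a one-third share that depends on how 'this hospital' is read.

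**What to change.** Reconcile the Visit Plan with sections 2.1.4, 5.3.3 (Subject Loss to Follow-up) and 9 as follows.

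1. Define 'this hospital' as each participating centre.
2. For every patient in the survival analysis, wherever treated, record vital status with date of death and progression status with date, at one fixed interval common to all three centres. Take these from the records where they are current, and otherwise through the telephone follow-up that already exists.
3. Set one common data cut-off and censor at the last confirmed contact.
4. In section 5.3.3, separate loss for survival from loss for diagnosis. That section excludes patients lost to follow-up from the diagnostic analysis. Once survival calls are added, a patient whose pathology is in hand should not drop out of the primary analysis because a later call went unanswered.

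The cost is a few more calls per patient (more for long survivors if follow-up runs on) and ethics approval of the amendment, which section 6.1 requires. It is best done early in recruitment, because dates that are not collected may not be recoverable later.

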1.1 Current Status of Lung Cancer

Lung cancer is one of the most common malignant tumors worldwide, with its mortality rate ranking first among all cancers. According to the latest epidemiological data, the five-year survival rate of lung cancer is only 19.7%, indicating that the disease poses a serious threat to human health [1]. The incidence of lung cancer varies significantly across different regions, particularly in China, where both the incidence and mortality rates are higher than the global average. In some areas, such as certain coal mining regions in Yunnan, the incidence of lung cancer has significantly increased due to environmental pollution [2].

1.2 Research Progress of 18F-FAPI PET/CT in the Diagnosis of Lung Cancer

In recent years, 18F-FAPI PET/CT, as an emerging imaging technology, has demonstrated excellent sensitivity and specificity in the diagnosis of lung cancer. Studies have shown that 18F-FAPI PET/CT exhibits significant advantages in detecting lung adenocarcinoma (LAD). A prospective study revealed that 18F-FAPI PET/CT achieved a 100% detection rate for primary tumors. Moreover, in lesions within lymph nodes, pleura, bones, and other tissues, the maximum standard uptake value (SUVmax) of 18F-FAPI was generally higher than that of 18F-FDG. Additionally, 18F-FAPI PET/CT identified more lesions in the detection of lymph nodes, brain, and pleural lesions [3]. These findings indicate that 18F-FAPI PET/CT holds important clinical value in the early diagnosis and staging of lung cancer. Particularly in cases with low 18F-FDG affinity, 18F-FAPI PET/CT provides clearer imaging and higher SUVmax values [4]. Meanwhile, mediastinal and hilar lymph nodes still exhibit a high false-positive rate on 18F-FDG PET, whereas 18F-FAPI PET/CT enhances the specificity of lymph node diagnosis.

Furthermore, 18F-FAPI PET/CT has demonstrated high diagnostic efficacy in the staging evaluation of lung cancer patients. Studies have found that 18F-FAPI PET/CT achieves a diagnostic efficacy of 95.3% in T-stage classification, significantly superior to the 57.1% efficacy of 18F-FDG PET/CT [5]. This difference may be attributed to the specific binding of 18F-FAPI to fibroblast activation protein (FAP) in the tumor microenvironment, which enhances its sensitivity in tumor tissue recognition.

In comparative studies, 18F-FAPI PET/CT has also been found to be a viable alternative to 18F-FDG PET/CT in certain scenarios, particularly for tumors with low 18F-FDG affinity or cases with ambiguous imaging findings. Although 18F-FDG PET/CT remains the preferred imaging modality in specific situations, the potential of 18F-FAPI PET/CT as a complementary imaging approach should not be overlooked [4]. This complementarity offers novel insights into the comprehensive diagnosis of lung cancer, especially in the management of complex cases.

1.3 Current Challenges

1.3.1 The diagnostic efficacy of 18F-FAPI PET/CT in different lung cancer subtypes requires further validation

Although existing studies have demonstrated the significant efficacy of 18F-FAPI PET/CT in certain tumor types, its diagnostic performance across different lung cancer subtypes remains to be further validated. Significant biological and clinical differences exist among various lung cancer subtypes, particularly non-small cell lung cancer (NSCLC) and small cell lung cancer (SCLC). Research indicates that the clinical validation of 18F-FAPI PET/CT for identifying lung cancer subtypes has not been sufficiently established. For instance, one study revealed that the sensitivity and specificity of 18F-FAPI PET/CT in detecting lung cancer differ from those of conventional 18F-FDG PET/CT, especially regarding tumor burden and metabolic activity across different subtypes [6]. Therefore, the specific diagnostic capabilities for various lung cancer subtypes still require validation through large-scale clinical trials.

1.3.2 Consistency of Imaging Evaluation Criteria in the Assessment of Treatment Efficacy for Lung Cancer

Currently, the most commonly used imaging evaluation standard is the Response Evaluation Criteria in Cancer (RECIST 1.1), which primarily relies on unidimensional measurements of tumor size. However, the limitation of RECIST 1.1 lies in its failure to adequately account for the biological characteristics of tumors and the complexity of treatment responses. For instance, the introduction of immunotherapy has made tumor response patterns more complex, potentially leading to temporary increases in tumor volume, which may be misinterpreted as disease progression under the traditional RECIST criteria. Consequently, 18F-FAPI PET/CT-based evaluation standards such as iRECIST have emerged to better reflect the efficacy of immunotherapy and account for the dynamic changes in tumor responses [7].

